Clinical Trial Protocol: VISTA-2 / 19-110-0011

Protocol Title: A Phase 3, Multi-Center, Randomized, Double-Masked, Placebo-Controlled Clinical Study to Assess the Safety and Efficacy of SkQ1 Ophthalmic Solution in the Environment and During Challenge in the Controlled Adverse Environmental (CAE[®]) Model for the Treatment of Dry Eye Syndrome

Protocol Number: VISTA-2 / 19-110-0011

Study Phase: 3

Product Name: SkQ1 Ophthalmic Solution

IND Number: 113433

Indication: Dry Eye Syndrome (DES)

Investigators: Multi-Center

Sponsor: Mitotech, SA
[name]
[name]
Luxembourg

Contract Research Organization: Ora. Inc.
[name]
[name]

IRB: Alpha IRB
[name]
[name]
[name]

Date

Original Protocol: Version 1.0 4 November 2019

Confidentiality Statement

This protocol contains confidential, proprietary information of Ora, Inc. and/or Mitotech. Further dissemination, distribution or copying of this protocol or its contents is strictly prohibited.

SPONSOR PERSONNEL

[REDACTED]	[REDACTED]
[REDACTED]	[REDACTED]
[REDACTED]	[REDACTED]

ORA PERSONNEL

[REDACTED]	[REDACTED]
[REDACTED]	[REDACTED]
[REDACTED]	[REDACTED]

SYNOPSIS

Protocol Title:	A Phase 3, Multi-Center, Randomized, Double-Masked, Placebo-Controlled Clinical Study to Assess the Safety and Efficacy of SkQ1 Ophthalmic Solution in the Environment and During Challenge in the Controlled Adverse Environmental (CAE [®]) Model for the Treatment of Dry Eye Syndrome
Protocol Number:	VISTA-2 / 19-110-0011
Study Drug:	1) 1.55 µg/mL SkQ1 ophthalmic solution 2) Placebo SkQ1 ophthalmic solution (Vehicle of SkQ1 ophthalmic solution)
Study Phase:	3
Study Objective:	The objective of this study is to compare the safety and efficacy of SkQ1 ophthalmic solution to placebo for the treatment of the signs and symptoms of dry eye syndrome.
Overall Study Design	
Structure:	Multi-center, double-masked, randomized, placebo-controlled study
Duration:	An individual subject's participation is estimated to be approximately 9 weeks (63 days)
Controls:	Placebo SkQ1 ophthalmic solution (Vehicle of SkQ1 ophthalmic solution)
Dosage/Dose Regimen:	Subjects eligible to be randomized will receive one of the following treatments to be administered bilaterally as 1-2 drops █████ for 56 days (from Visit 2 to Visit 5): 1) 1.55 µg/mL SkQ1 ophthalmic solution 2) Placebo SkQ1 ophthalmic solution (Vehicle) During a 7-day study run-in period (beginning at the end of Visit 1 for the purpose of subject selection) prior to randomization, all subjects will receive 1-2 drops of Placebo SkQ1 ophthalmic solution (Vehicle) bilaterally █████
Summary of Visit Schedule:	5 visits over the course of approximately 9 weeks 
 • Visit 1 = Day -7 -2/+1 days, Screening • Visit 2 = Day 1, Baseline, Screening Confirmation, Randomization and Initiation of Double-Masked Treatment • Visit 3 = Day 29 ± 2 days • Visit 4 = Day 43 ± 2 days

	
 • Visit 5 = Day 57 ± 4 days, 8-Week CAE[®] Test, End of Double-Masked Treatment • [REDACTED]

Measures Taken to Reduce Bias:
	
This is a double-masked study. Subjects will be assigned to treatment groups using stratified random sampling [REDACTED]

Study Population Characteristics
	

Number of Subjects:
	
Approximately [REDACTED] subjects will be screened to enroll approximately 600 (300 active : 300 placebo) subjects

Condition/Disease:
	
Dry Eye Syndrome

Inclusion Criteria:
	
Subjects must:
 
 a. Be at least 18 years of age; b. Provide written informed consent; c. Have a subject-reported history of dry eye for at least 6 months prior to Visit 1; d. Have a history of use or desire to use eye drops for dry eye symptoms within 6 months of Visit 1; e. [REDACTED] f. [REDACTED] g. [REDACTED] h. [REDACTED] i. [REDACTED]

	
j. [REDACTED]
 
k. Have at least one eye (the same eye) satisfy all criteria for f, g, h, i, and j above.


Exclusion Criteria:
	
Subjects must not:
 
 a. Have previously been exposed to SkQ1 ophthalmic; b. Have any clinically significant slit-lamp findings at Visit 1 that may include active blepharitis, meibomian gland dysfunction (MGD), lid margin inflammation or active ocular allergies that require therapeutic treatment, and/or in the opinion of the investigator may interfere with study parameters; c. Be diagnosed with an ongoing ocular infection (bacterial, viral, or fungal), or active ocular inflammation (e.g. follicular conjunctivitis) at Visit 1; d. Have worn contact lenses within 7 days of Visit 1 or anticipate using contact lenses during the study; e. Have used any eye drops within 2 hours of Visit 1; f. Have previously had laser-assisted in situ keratomileusis (LASIK) surgery within the last 12 months; g. Have used Restasis[®], Xiidra[®] or CEQUA[™] within 60 days of Visit 1; h. Have had any ocular and/or lid surgeries within 6 months of Visit 1 or any planned over the study period; i. Be using or anticipate using temporary punctal plugs during the study that have not been stable within 30 days of Visit 1; j. Be currently taking any topical ophthalmic prescription (including medications for glaucoma) or over-the-counter (OTC) solutions, artificial tears, gels or scrubs, and cannot discontinue these medications for the duration of the trial (excluding medications allowed for the conduct of the study); k. Have corrected visual acuity greater than or equal to logMAR+0.7 as assessed by Early Treatment of Diabetic Retinopathy Study

	
(ETDRS) scale in both eyes at Visit 1;
 
l. Have an uncontrolled systemic disease;m. Be a woman who is pregnant, nursing or planning a pregnancy;n. Be unwilling to submit a urine pregnancy test at Visit 1 and Visit 5 (or early termination visit) if of childbearing potential. Non-childbearing potential is defined as a woman who is permanently sterilized (e.g. has had a hysterectomy or bilateral tubal ligation or bilateral oophorectomy), or is post-menopausal (without menses for 12 consecutive months);o. Be a woman of childbearing potential who is not using an acceptable means of birth control; acceptable methods of contraception include: hormonal – oral, implantable, injectable, or transdermal contraceptives; mechanical – spermicide in conjunction with a barrier such as a diaphragm or condom; IUD; or surgical sterilization of partner. For non-sexually active females, abstinence may be regarded as an adequate method of birth control; however, if the subject becomes sexually active during the study, she must agree to use adequate birth control as defined above for the remainder of the study;p. q. Have a condition or be in a situation which the investigator feels may put the subject at significant risk, may confound the study results, or may interfere significantly with the subject's participation in the study;r. Be currently enrolled in an investigational drug or device study or have used an investigational drug or device within 30 days of Visit 1;s. Be currently using any medication known to cause ocular drying that is not used on a stable dosing regimen for at least 30 days prior to Visit 1;t. Be currently using any hormone replacement therapy that is not used on a stable dosing regimen for at least 30 days prior to Visit 1 and during the study;
--	---

	u. Be unable or unwilling to follow instructions, including participation in all study assessments and visits.
Study Formulations and Formulation Numbers:	Run-in: Placebo to be supplied by the sponsor. Study Drug: Batch/lot information for SkQ1 ophthalmic solution (1.55µg/mL and Placebo) to be supplied by the sponsor.
Evaluation Criteria	
Efficacy Measures:	Primary Efficacy Measures: The primary endpoints will be tested in a hierarchical fixed sequence in the following order: 
• Change from baseline (Visit 2) in Ocular Discomfort at Visit 5 (Day 57) [REDACTED]• Change from baseline (Visit 2) in conjunctival fluorescein staining (sum of temporal and nasal regions) at Visit 5 (Day 57) [REDACTED] Key Secondary Efficacy Measures: The key secondary efficacy endpoints will be tested in a hierarchical fixed sequence in the following order: 
1. Change from baseline (Visit 2) in Ocular Discomfort at Visit 3 (Day 29) [REDACTED]2. Change from baseline (Visit 2) in conjunctival fluorescein staining (sum of temporal and nasal regions) at Visit 4 (Day 43) [REDACTED]

Safety Measures:	
• Visual acuity (ETDRS);• Slit-lamp biomicroscopy;• Adverse event query;• Dilated funduscopy• Intraocular pressure
Other:	
• N/A
General Statistical Methods and Types of Analyses Analysis Populations 
• Intent-to-Treat Population – The intent-to-treat (ITT) population includes all randomized subjects. The primary and secondary efficacy analyses will be performed on the ITT population. Subjects in the ITT population will be analyzed as randomized.• Per-Protocol Population – The per-protocol (PP) population excludes subjects with significant protocol deviations or who do not complete the study. Protocol deviations will be assessed prior to database lock and unmasking. Subjects in the PP population will be analyzed as treated.• Safety Population – The safety population will include all subjects receiving treatment from whom at least one safety measurement is obtained following the first dose of study drug. The safety population will be analyzed for all safety assessments. Subjects in the Safety population will be analyzed as treated. 
In addition, the following populations are defined for the primary and key secondary analysis of conjunctival fluorescein staining:
 
ITTCFS Population – [REDACTED]
 
PPCFS Population – [REDACTED]
 Sample Size 
To address the multiple primary efficacy variables employed in this study, the sample size calculations have been based on a hierarchical structure. In order to test a variable,
	

the preceding variable(s) must have shown statistically significant improvements versus placebo using a two-sided significance level of 0.05. Using these strategies, the Type I error rate will be maintained at the 0.05 significance level for the primary efficacy variables.

This study is expected to enroll 300 subjects in the active treatment arm and 300 subjects in the placebo group [REDACTED]

[REDACTED]

[REDACTED] enrollment of 284 patients per group would be required for 90% power for each endpoint to detect the differences between the active treatment group and placebo group.

Primary Efficacy Analyses

Efficacy analyses will be performed on the ITT and ITTCFS populations, for Ocular Discomfort and conjunctival fluorescein staining endpoints, respectively. Supportive analyses will be performed on the PP and PPCFS populations, for Ocular Discomfort and conjunctival fluorescein staining endpoints, respectively.

Primary efficacy endpoints are:

- Change from baseline (Visit 2) in Ocular Discomfort in the worst eye at Visit 5 (Day 57) [REDACTED]
- Change from baseline (Visit 2) in conjunctival fluorescein staining (sum of temporal and nasal regions) in the worst eye at Visit 5 (Day 57) [REDACTED]

The primary efficacy endpoint of conjunctival fluorescein staining (sum of temporal and nasal regions) will be tested in the pre-specified subgroup [REDACTED]

The primary efficacy endpoints will be analyzed using an analysis of covariance (ANCOVA) model [REDACTED]

[REDACTED] The adjusted least squares means and their

standard errors (SEs) will be presented along with their two-sided 95% confidence intervals (CIs) for each treatment group and the difference between the active treatment group and the placebo treatment group. In addition, a two-sample t-test will be used to compare the active and placebo groups in the change from baseline at Visit 5 [REDACTED]. The mean difference, SD for the difference, and the 95% CI for the difference will be presented. A two-sided p-value < 0.05 will be considered statistically significant.

The primary analyses for both primary endpoints will be conducted on the ITT and ITTCFS populations for Ocular Discomfort and conjunctival fluorescein staining, respectively, using the Markov Chain Monte Carlo (MCMC) multiple imputation method to impute missing data. [REDACTED]

[REDACTED] Sensitivity analyses for the ocular discomfort endpoint will also be performed using Last Observation Carried Forward (LOCF) method on the ITT population as well as with the observed data only for both the ITT and PP populations. Sensitivity analyses for the conjunctival fluorescein staining endpoint will be performed using LOCF on the ITTCFS population as well as with the observed data only for both the ITTCFS and PPCFS populations. Sensitivity analyses using LOCF and observed data only will include Wilcoxon rank sum tests.

Key Secondary Efficacy Analyses

The key secondary efficacy endpoint of conjunctival fluorescein staining at Visit 4 (Day 43) will be tested in the ITTCFS population; other key secondary efficacy endpoints will be tested in the full ITT population.

Imputation will not be applied for any missing data in the key secondary efficacy endpoints.

Analyses will use ANCOVA models with baseline values included as covariates. Two-sample t-tests and Wilcoxon rank sum tests will be performed as sensitivity analyses.

Sensitivity analyses of the conjunctival fluorescein staining endpoint will be performed using the PPCFS population with observed data only. Sensitivity analyses of the other key secondary endpoints will be performed using the PP population with observed data only.

Exploratory Efficacy Analyses

Exploratory efficacy analyses will be analyzed on the ITT population using observed data. Imputation will not be applied for any missing data in the exploratory efficacy endpoints.

Analyses will use ANCOVA models with baseline values included as covariates, two-sample t-tests, and Wilcoxon rank sum tests. [REDACTED]

Safety Variables

Frequencies and percentages of subjects with treatment-emergent adverse events (TEAEs), serious TEAEs, and TEAEs causing premature treatment discontinuation will be provided by treatment group. An AE is treatment emergent if it occurs or worsens

after the first dose of study treatment. Furthermore, frequencies will be given of subjects with TEAEs by system organ class and preferred term for the following categories of AEs:

- All TEAEs
- TEAEs at least possibly related to study treatment
- TEAEs leading to study treatment discontinuation
- Serious TEAEs (SAEs)
- By maximal severity
- By study day of onset

Separate analyses will be performed for ocular and non-ocular AEs.

1 INTRODUCTION

Dry eye syndrome (DES), also known as Keratoconjunctivitis sicca (KCS), is a multifactorial disease of the tears and ocular surface; symptoms include discomfort, visual disturbance, and tear film instability, with the potential for exposure of and damage to the ocular surface. The condition is accompanied by increased osmolarity of tears and inflammation of the ocular surface. Symptoms can be caused by defects in the aqueous, lipid, and/or mucin layers of the tear film¹. Current therapies for dry eye are only palliative, mostly focusing on replacement of tears to reduce symptoms. Only three approved products are available in the USA currently: Restasis[®] (Cyclosporine Ophthalmic Emulsion, Allergan, Irvine, California, USA), CEQUA[™] (cyclosporine ophthalmic solution, Sun Pharma, Princeton, NJ, USA) and Xiidra[®] (lifitigrastr ophthalmic solution, Shire US, Inc., Lexington, MA, USA).

Oxidative mechanisms are also believed to play an important role in the pathogenesis of age-related eye disease such as DES. Consequently, many investigations have focused on whether vitamins and trace minerals with antioxidant properties help prevent the onset or progression of DES.

SkQ1 is a novel compound and powerful antioxidant. Given its chemical properties, SkQ1 and related compounds have been shown to be active in a variety of animal models of illness believed to involve free radical damage. These include rat models of H₂O₂ and ischemia-induced heart arrhythmia, heart infarction, kidney ischemia, and stroke studied both ex vivo and in vivo.¹ In addition, SkQ1 has been found to provide benefit in a number of models of eye diseases, including DES²⁻⁶.

[REDACTED]

[REDACTED]

[REDACTED]

[REDACTED]

[REDACTED]

[REDACTED]

[REDACTED]

[REDACTED]

[REDACTED]

[REDACTED]

2 STUDY OBJECTIVES

The objective of this study is to compare the safety and efficacy of SkQ1 ophthalmic solutions to placebo for the treatment of the signs and symptoms of DES.

3 CLINICAL HYPOTHESES

The clinical hypotheses for this study is that SkQ1 ophthalmic solution 1.55µg/mL is superior to placebo for the primary endpoints of signs and symptoms, as follows:

- Subjects receiving SkQ1 ophthalmic solution will have a statistically significantly lower mean change from baseline (Visit 2) in Ocular Discomfort at Visit 5 (Day 57) [REDACTED]
- Subjects receiving SkQ1 ophthalmic solution will have a statistically significantly lower mean change from baseline (Visit 2) in conjunctival fluorescein staining (sum of temporal and nasal regions) at Visit 5 (Day 57) [REDACTED]

4 OVERALL STUDY DESIGN

See synopsis.

5 STUDY POPULATION

5.1 Number of Subjects (approximate)

It is estimated that approximately [REDACTED] subjects will be screened to enroll approximately 600 (300 active: 300 placebo) subjects. Subjects will be randomized in a 1:1 ratio to 1.55 µg/mL SkQ1 or placebo.

5.2 Study Population Characteristics

All subjects must be at least 18 years of age, of either gender, and of any race, and must meet all inclusion criteria and none of the exclusion criteria.

5.3 Inclusion Criteria

Subjects must:

- a. Be at least 18 years of age;
- b. Provide written informed consent;
- c. Have a subject-reported history of dry eye for at least 6 months prior to Visit 1;
- d. Have a history of use or desire to use eye drops for dry eye symptoms within 6 months of Visit 1;
- e. [REDACTED]
- f. [REDACTED]
- g. [REDACTED]
- h. [REDACTED]
- i. [REDACTED]
- j. [REDACTED]
- k. Have at least one eye (the same eye) satisfy all criteria for f, g, h, i, and j above.

5.4 Exclusion Criteria

Subjects must not:

- a. Have been exposed to SkQ1 ophthalmic solution;
- b. Have any clinically significant slit lamp findings at Visit 1 that may include active blepharitis, meibomian gland dysfunction (MGD), lid margin inflammation or active ocular allergies that require therapeutic treatment, and/or in the opinion of the investigator may interfere with study parameters;
- c. Be diagnosed with an ongoing ocular infection (bacterial, viral, or fungal), or active ocular inflammation (e.g. follicular conjunctivitis) at Visit 1;
- d. Have worn contact lenses within 7 days of Visit 1 or anticipate using contact lenses during the study;
- e. Have used any eye drops within 2 hours of Visit 1;
- f. Have previously had laser-assisted *in situ* keratomileusis (LASIK) surgery within the last 12 months;
- g. Have used Restasis[®], Xiidra[®] or CEQUA[™] within 60 days of Visit 1;
- h. Have had any ocular and/or lid surgeries within 6 months of Visit 1 or any planned over the study period;
- i. Be using or anticipate using temporary punctal plugs during the study that have not been stable within 30 days of Visit 1;
- j. Be currently taking any topical ophthalmic prescription (including medications for glaucoma) or over-the-counter (OTC) solutions, artificial tears, gels or scrubs, and cannot discontinue these medications for the duration of the trial (excluding medications allowed for the conduct of the study);
- k. Have corrected visual acuity greater than or equal to logMAR+0.7 as assessed by Early Treatment of Diabetic Retinopathy Study (ETDRS) scale in both eyes at Visit 1;
- l. Have an uncontrolled systemic disease;
- m. Be a woman who is pregnant, nursing or planning a pregnancy;
- n. Be unwilling to submit a urine pregnancy test at Visit 1 and Visit 5 (or early termination visit) if of childbearing potential. Non-childbearing potential is defined as a woman who is permanently sterilized (e.g. has

had a hysterectomy or bilateral tubal ligation or bilateral oophorectomy), or is post-menopausal (without menses for 12 consecutive months);

- o. Be a woman of childbearing potential who is not using an acceptable means of birth control; acceptable methods of contraception include: hormonal – oral, implantable, injectable, or transdermal contraceptives; mechanical – spermicide in conjunction with a barrier such as a diaphragm or condom; IUD; or surgical sterilization of partner. For non-sexually active females, abstinence may be regarded as an adequate method of birth control; however, if the subject becomes sexually active during the study, she must agree to use adequate birth control as defined above for the remainder of the study;
- p. 
- q. Have a condition or be in a situation which the investigator feels may put the subject at significant risk, may confound the study results, or may interfere significantly with the subject's participation in the study;
- r. Be currently enrolled in an investigational drug or device study or have used an investigational drug or device within 30 days of Visit 1;
- s. Be currently using any medication known to cause ocular drying that is not used on a stable dosing regimen for at least 30 days prior to Visit 1;
- t. Be currently using any hormone replacement therapy that is not used on a stable dosing regimen for at least 30 days prior to Visit 1 and during the study;
- u. Be unable or unwilling to follow instructions, including participation in all study assessments and visits.

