8.1.2 Informed Consent

Prior to a subject's participation in the trial (i.e., prior to changes in a subject's medical treatment and/or prior to study related procedures), the study will be discussed with each subject, and subjects wishing to

participate must give written informed consent using an informed consent form (ICF). The informed consent form must be the most recent version that has received approval/favorable review by a properly constituted Institutional Review Board (IRB).

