8.1.3 Washout Intervals

Prohibited medications, treatments, and activities are outlined in the Exclusion Criteria (Section 5.4).

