8.2.1 Prohibited Medications/Treatments

Disallowed medications/treatments during the study are outlined in the Exclusion Criteria (Section 5.4).

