8.3 Examination Procedures

8.3.1 Procedures to be Performed at Each Study Visit with Regard to Study Objective(s)

The following procedures will be performed (see Appendix 2 for description):

Visit 1 (Day -7 -2/+1 days): Screening

- Informed consent / Health Information Portability and Accountability Act (HIPAA);
- Demographic data and medical / medication history;
- Urine pregnancy test (for females of childbearing potential);
- [REDACTED] Ocular Discomfort Scale;
- [REDACTED] Ocular Discomfort Scale & 4-Symptom Questionnaire;
- [REDACTED]
- Visual acuity;
- Review of qualification criteria;
- Slit-lamp biomicroscopy;
- [REDACTED] [REDACTED]
- [REDACTED]
- Tear Film Break-up Time (TFBUT);
- Fluorescein staining [REDACTED]

- [REDACTED];
- [REDACTED]
- [REDACTED]
- Intraocular pressure;
- Dilated funduscopy;
- Review of qualification criteria;
- Adverse event query;
- Dispensation of run-in (RUN-IN) for [REDACTED] until Visit 2;
 - [REDACTED]
- [REDACTED]
 - [REDACTED]
- Dispensation of diaries and subject instructions;
 - [REDACTED]
 - [REDACTED]
 - [REDACTED]
 - [REDACTED]
- Qualified subjects will be scheduled for Visit 2.

Visit 2 (Day 1): Baseline/Screening Confirmation/ Randomization and Initiation of Double-Masked Treatment

- Collection and review of run-in (RUN-IN) and subject diaries;
- [REDACTED]
- Medical/medication history update;
- Adverse event query;
- [REDACTED] Ocular Discomfort Scale;

- [REDACTED] Ocular Discomfort Scale & 4-Symptom Questionnaire;
- [REDACTED]
- Visual acuity;
- Slit-lamp biomicroscopy;
- [REDACTED]
- [REDACTED]
- TFBUT;
- Fluorescein staining [REDACTED]
- [REDACTED] [REDACTED]
- [REDACTED]
- [REDACTED]
- Review of qualification criteria;
- Randomization;
- Dispensation of study drug kit according to randomization for [REDACTED] until Visit 3;
- [REDACTED]
 - [REDACTED]
- [REDACTED]
- [REDACTED]
- [REDACTED]
 - [REDACTED]
 - [REDACTED]
 - [REDACTED]
- Adverse event query;
- Schedule subjects for Visit 3.

○ [REDACTED]

- Adverse event query;
- Schedule subjects for Visit 4.

[REDACTED]

■ [REDACTED]

Visit 4 (Day 43 ± 2 days): 4-Week Follow-up

- Collection and review of study drug and subject diaries;
- [REDACTED]
- Medical / medication history update;
- Adverse event query;
- [REDACTED] Ocular Discomfort Scale;
- [REDACTED] Ocular Discomfort Scale & 4-Symptom Questionnaire;
- [REDACTED]
- Visual acuity;
- Slit-lamp biomicroscopy;
- [REDACTED] [REDACTED]
- [REDACTED]
- TFBUT;

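### As worded, exclusion j does not bar a glaucoma-drop user who can stop treatment, and the readable schedule measures intraocular pressure only at Visits 1 and 5

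*Combined protocol and SAP*

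**What the plan says.** Exclusion j in Section 5.4, repeated in the synopsis, joins two conditions with 'and'. The subject is currently using a topical ophthalmic product, "including medications for glaucoma) or over-the-counter (OTC) solutions, artificial tears, gels or scrubs, and cannot discontinue these medications for the duration" of the trial. Medications needed for study conduct are carved out, but no list of them is readable.

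The other medication rules lead back to the same place. On prohibited treatments, Section 8.2.1 says "Disallowed medications/treatments during the study are outlined in the Exclusion Criteria (Section 5.4"), and Section 8.1.3 on washout makes the same cross-reference without setting an interval. Exclusion e bars only those who "Have used any eye drops within 2 hours of Visit 1". Section 8.1.2 puts consent ahead of any change in the subject's "medical treatment and/or prior to study related procedures".

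In Section 8.3.1, Visit 1 lists "Intraocular pressure" and dilated funduscopy, followed by "Review of qualification criteria". Qualification is reviewed again at Visit 2, before randomization. IOP next appears in readable text at Visit 5.

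**The concern.** The protocol names glaucoma medication and then gives it the same test as artificial tears and lid scrubs: stop it, or be excluded. A user who can stop passes j and must then stay off the drops for the whole trial. No readable criterion excludes glaucoma or ocular hypertension as a diagnosis, and none sets an IOP limit.

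Whether someone comes off pressure-lowering treatment for a dry eye trial is therefore left to the investigator. The pressure available for that decision is probably one measured while the drops were still working, so it would not show how the eye behaves untreated. Section 9.2 itself gives optic nerve damage as an example of a serious sight-threatening event. Only individual subjects are at risk here; sample size, error rates and the treatment comparison are not involved.

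**Working it through.** **1. Who passes j.** Exclusion requires A (currently using the product) and B (cannot discontinue it). A user who can stop meets A but not B, so j does not exclude that person. Passing j is not the same as admission: inclusions e to j and exclusion p cannot be read, and exclusion q leaves room for investigator judgement.

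**2. What the Visit 1 IOP shows.** Treatment may not be changed before consent (8.1.2), only 2 hours without drops is required (exclusion e), and 8.1.3 adds no washout. The inference is that the Visit 1 pressure is a treated one. The qualification review that follows it has no untreated value to use. The Visit 2 review has no readable IOP.

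**3. Time between checks.** The inputs are the synopsis visit windows: Visit 1 at Day -7 (-2/+1), so Day -9 to -6; Visit 2 at Day 1; Visit 3 at Day 29 ± 2; Visit 5 at Day 57 ± 4. A 7-day run-in from Day -7 to Day 1 implies that there is no Day 0. The protocol's own duration is reproduced first: 7 days of run-in + 56 days of treatment = 63 days = 9.0 weeks, as in Section 8.8.

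| Interval | Nominal | Shortest | Longest |
|---|---|---|---|
| Visit 1 to Visit 2 | 7 | 6 (Day -6 to 1) | 9 (Day -9 to 1) |
| Visit 1 to Visit 5 | 7 + 56 = 63 | 6 + 52 = 58 | 9 + 60 = 69 |
| Visit 1 to Visit 3 | 7 + 28 = 35 | 6 + 26 = 32 | 9 + 30 = 39 |
| Visit 3 to Visit 5 | 57 - 29 = 28 | 53 - 31 = 22 | 61 - 27 = 34 |

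The first two rows describe the readable schedule. The last two apply only if the unseen Visit 3 list or Appendix 1 includes IOP at Visit 3.

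**4. Could a redaction hide an IOP at Visit 2 or 4?** At Visit 1, three blacked-out lines follow fluorescein staining, and IOP is a further, open line after them. At Visits 2 and 4 there are also three blacked-out lines after fluorescein staining, with no open IOP line. IOP is left legible at Visits 1 and 5. A hidden IOP at Visit 2 or 4 is therefore unlikely, but this is circumstantial: equal line counts do not prove equal content, and both visits have other blacked-out lines.

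**The case against.** The strongest reply is that the hazard depends on text that cannot be seen. One hidden line, such as exclusion p or an IOP check at Visit 3, could remove or shrink it. That stands as a limit on the conclusion: 63 days is the gap in the readable schedule and is not established as the gap in the trial.

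A second reply is that j exists to exclude. A patient who needs glaucoma drops is one who cannot discontinue them, and any sensible investigator would read it as 'cannot safely discontinue'. Many would, but the text does not say so, and glaucoma drops sit in the same clause as products whose withdrawal carries no such risk.

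Third, safeguards exist. Exclusion q bars subjects judged to be at significant risk. Visual acuity, slit lamp and adverse event queries are readable at Visits 2 and 4. IOP may be measured at unscheduled visits. Section 5.5 permits withdrawal for safety, and early termination brings the Visit 5 safety evaluations forward. These are real protections, but none is a readable scheduled pressure measurement after the drops are stopped.

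Two smaller points also stand. The study-conduct carve-out could in principle let the drops continue, although nothing readable says so. That the Visit 1 pressure is a treated one is an inference.

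**Conclusion.** The concern holds as a low-severity point of patient safety, with moderate confidence. On its wording, j admits a current user of topical glaucoma medication who can stop it, and no other readable rule closes that gap. Such a subject could go 63 days (58 to 69) between readable IOP checks, or 35 days (32 to 39) to a first reading off drops if Visit 3 includes one. The Visit 2 qualification review, 7 days (6 to 9) after Visit 1, precedes either reading.

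This rests on three assumptions: that no unreadable criterion bars these subjects, that the investigator does not exclude them, and that drops continue until consent at Visit 1. The documents do not say how many subjects would be affected; it may be none. Efficacy inference is untouched.

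**What to change.** In Section 5.4 j and its synopsis copy, take glaucoma medication out of the 'cannot discontinue' condition. Begin j with an unconditional limb, for example: 'be currently using any topical IOP-lowering (glaucoma) medication; or'. Then keep the present wording for any other topical ophthalmic product, without the glaucoma parenthesis. Keeping both limbs under j avoids relettering.

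The cost is wording in two places and the loss at screening of any candidates on these drops, a number the documents do not give. The enrollment target of about 600 stays, so they would be replaced. No procedure or analysis changes. If an unreadable criterion already excludes these users, the edit only makes j consistent with it. It does not cover someone who stopped drops shortly before Visit 1; a look-back period would, but its length is a clinical choice for the sponsor.
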